The organizations were chosen for geographic, socioeconomic, and racial/ethnic diversity of patients; and for diversity in the size and type of health care delivery system: fee for service, capitated HMO, integrated, and academic. We plan to enroll approximately 35,200 participants with small nodules at these sites during a 28-month period, providing sufficient statistical power for the study aims. We will include consecutive patients with small nodules, so the assembled cohort will reflect the diversity of patients seen at all participating institutions. The large number

and types of facilities and highly diverse populations will provide results that are generalizable to the broader U.S. population.

Inclusion Criteria: The target population includes adults with small lung nodules, who typically would be managed by CT surveillance in usual clinical practice. Thus, we will enroll all adult patients aged ≥ 35 years with at least one newly identified nodule measuring ≤ 15 mm in average cross-sectional diameter on chest CT. We increased the original age threshold from 21 years to 35 years, because lung nodules and (especially) lung cancer are extremely rare in individuals younger than age 35, and the new Fleischner Society guidelines are specifically designed for individuals who are 35 years-old or older. The intention to treat population will include patients with nodules of this size who do or do not undergo surveillance imaging. We anticipate most patients will be >50 years old, as both CT use and nodule detection are more common in older patients. Further, because CT scanning is used more frequently in persons with chronic illness, we expect a high proportion of patients to have comorbidities. To accommodate the implementation of lung cancer screening in many settings, we will include individuals with nodules detected either incidentally or by screening at 6 participating sites: HealthPartners, Kaiser Permanente (Colorado, Northwest, Southern California), Medical University of South Carolina, and UC Davis.

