The original protocol for more intensive imaging was based on published guidelines from the Fleischner Society (2005, 2013) and the National Comprehensive Cancer Network (NCCN), while most of the recommendations for less intensive imaging were derived from the American College of Radiology's Lung CT Screening Reporting and Data System (Lung-RADS). However, Fleischner Society and NCCN recommendations were recently revised, providing an ideal opportunity to compare the (more intensive) existing recommendations with the (less intensive) newly revised recommendations, a comparison that is most relevant to current clinical practice.

The surveillance protocols are summarized in Tables 2 and 3. Additional details are provided in Appendix Tables C1-C3.

Table 2: Group A, More Intensive Surveillance					
Nodule characteristics	Nodule size (mm)	Surveillance times (months from index CT)	Optional	For screening-detected nodules (if different)	Source
Solid	≤4	12		12, 24	
	>4 to ≤6	6, 18			Fleischner, 2005
	>6 to ≤8	3, 9, 24		3, 9, 21	
	>8	3, 9, 24	PET/CT, biopsy	3, 9, 21	
Solitary Part-Solid	Any size, solid component ≤5	3, 15, 27, 39			
	Any size, solid component ≥5	3 (If persists, biopsy or resect)			Fleischner, 2013
Solitary Non-solid (GGN)	<5	None		12, 24	
	>5	3, 15, 27, 39			Fleischner, 2013
Multiple Part- or Non-solid	≤5 GGN	24, 48			
	>5 GGN	3, 15, 27, 39			Fleischner, 2013
	“Dominant”	3 (If persists, biopsy or resect)			

Table 3: Group B, Less Intensive Surveillance

Nodule characteristics	Nodule size (mm)	Surveillance times (months from index CT)	Optional	For screening-detected nodules (if different)	Source
Solid	<6	None	12	12, 24	Fleischner (2017)
	≥6 to ≤8	12, 24			
	>8	3, 15, 27	PET/CT, biopsy		
Part-solid	<6	None		12, 24	Fleischner (2017)
	≥6 with solid component <6	6, 18, 30			
	≥6 with solid component ≥6	6 (if persists, biopsy or resect)			
Non-solid	<6	None		12, 24	
	≥6	12, 36		12, 24	
Multiple	Solid, largest <6	None	12	12, 24	
	Solid, largest ≥6	6, 18			
	Part- or Non-solid	6, 24	6 (If persists, biopsy or resect)		

The comparators selected will result in approximately 30% less imaging in the less intensive Group B. By using these guidelines as the foundation for the surveillance protocols to be compared, we will preserve the trial's equipoise, integrity and relevance now that the revised Fleischner Society recommendations have been released⁴⁸.

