that went into effect in 2013, CTDIvol and DLP must be reported in the radiology report and will be extracted from the electronic medical records. Because each site has developed their own technique for reporting the radiation dose metrics in the medical record, the technique for extracting these data will be locally determined. Effective dose, measured in milli-Sieverts (mSv), combines information about the radiation imparted to the patient, the scan location reflecting the organs irradiated, and the deleterious effect, primarily of developing cancer in the future. Effective dose increases with the dose length product and is a function of the radio-sensitivity of the tissues irradiated. Effective dose will be calculated from the DLP for each examination using existing established conversion formulas, and summed over the study period for each enrollee.

Aim 4 Outcomes, Patient and Provider Adherence: We will measure adherence to the assigned surveillance protocol at the level of the interpreting radiologist, the ordering provider, and the individual patient. First, we will measure adherence with each recommended surveillance test: was the test recommended by the radiologist, ordered by the provider, and completed by the patient? Adherence at the patient and provider levels can be extracted from structured data in the EHR. To measure adherence at the level of the interpreting radiologist, we will review a sample of radiology transcripts to determine whether the recommendation for surveillance were present and per protocol. These analyses will provide granular information about adherence on a test-by-test basis and pinpoint the level of non-adherence. In addition, we will measure overall adherence, defined as completion of all recommended tests for surveillance at the individual patient level.

Data Management

The Data Coordinating Center (DCC) at UC Davis will be the central location for data management. The DCC will collect data captured locally at each participating site. This collected

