 - Pneumothorax requiring tube thoracostomy
 - Bleeding (pulmonary hemorrhage)
 - Acute respiratory failure
 - Acute renal failure
 - Allergic reaction to iodinated contrast material requiring hospitalization
 - Acute myocardial infarction
3. Cumulative radiation dose measured by DLP and effective dose

- Including radiation exposure from surveillance and diagnostic imaging following baseline CT scan through 2 years of follow-up (including 24 month exams).

Aim 4: Adherence with the recommended surveillance protocol

1. Radiologist adherence to assigned protocol
2. Physician adherence to ordering test
3. Patient adherence
 - a. Adherence to first recommended surveillance exam
 - b. Adherence to full protocol

Secondary endpoints:

Aim 1:

1. Proportion of lung cancers that are greater than 20mm, N0, MO
 - Measured as progression beyond AJCC 7th edition TNM stage of T1aN0M0 or AJCC 8th edition stage of T1bN0M)
2. Timeliness of lung cancer diagnosis
 - Measured as time from date of index CT scan to confirmed lung cancer diagnosis, defined as histologic confirmation via pathology, among individuals diagnosed with lung cancer.
3. Timeliness of lung cancer treatment
 - Measured as time from date of index CT scan to date of first treatment including surgery, radiotherapy or chemotherapy, among individuals diagnosed with lung cancer. If a patient receives no treatment, we will censor at end follow-up.
4. Overall survival of patients who prove to have a cancerous nodule,
 - Measured from date of index CT scan to death or censoring among individuals diagnosed with lung cancer.

Aim 2:

1. Patient general health status measured at 1-2 months, 13-24 months, and ≥ 25 months after nodule identification
2. Patient satisfaction with the evaluation process measured at 13-24 months and ≥ 25 months after nodule identification
3. Ordering specialist, primary care, and radiologist knowledge attitudes and beliefs about existing guidelines for pulmonary nodule evaluation measured at baseline
4. Provider satisfaction with the surveillance protocol and the evaluation process measured during the follow-up period

Aim 4: Adherence to use of low radiation-dose techniques

Hypotheses:

We specify the following hypotheses by aim:

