H3a: Among all participants with a lung nodule ≤ 15 mm, more intensive surveillance will be associated with greater nodule-related resource utilization, including more frequent use of CT scanning, PET scanning and invasive biopsy.

H3b: Among all participants with a lung nodule ≤ 15 mm, more intensive surveillance will be associated with a greater number of serious complications related to invasive procedures, including pneumothorax, pneumothorax requiring tube thoracostomy, bleeding, acute respiratory failure, acute renal failure and acute myocardial infarction.

H3c: Among all participants with a lung nodule ≤ 15 mm, more intensive surveillance will be associated with greater total exposure to diagnostic radiation than less intensive surveillance.

H4: Among all participants with a lung nodule ≤ 15 mm, more intensive surveillance will be associated with worse adherence to the surveillance protocol than less intensive surveillance, when measured at the level of the interpreting radiologist, the ordering provider and the patient.

Analysis Plan

In most cases, the unit of analysis will be the individual patient. All primary analyses will be by intention to treat, although we will also perform sensitivity analyses by surveillance imaging actually received. The intention to treat population will include all patients with qualifying nodules, even ones who do not undergo surveillance as the initial step in their evaluation (i.e., patients that proceed directly to tissue diagnosis). Sensitivity analyses will evaluate outcomes by strategy recommended and by surveillance imaging received.

Descriptive statistics will be generated for continuous variables (e.g., mean, standard deviation, median, range) and categorical variables (frequency) at baseline and follow-ups when appropriate. Bivariate analyses will include comparisons of means or medians (as appropriate) for continuously measured variables, cross tabulations of categorical variables, and Kaplan-Meier plots for time to event outcomes. Count outcomes, such as the number of procedure-related complications, will be treated as Poisson random variables. Analysis of time to

diagnosis, treatment, and survival will use Cox regression, after checking the proportionality assumption by creating log-minus-log plots.

H1a - Primary endpoint –lung cancer stage >T1a at diagnosis:

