Descriptive statistics will be generated for radiation exposure and frequency of follow-up CT scans and other nodule-related resource utilization will be obtained by site and study arm. For each type of nodule-related resource utilization, we will also create a binary variable to indicate whether a patient has any exam of that type (1 yes and 0 no) and obtain the corresponding frequency. For H3a, to examine whether among all participants with a lung nodule ≤ 15 mm, more intensive surveillance will be associated with a greater number of specific follow-up tests and types of follow-up tests (e.g., imaging, non-surgical biopsy, surgery), we will use mixed-effects Poisson regression model including random site effects to account for clustering of patients within sites. We will also model the frequency at which at least 1 specific follow-up test or type of follow-up test is performed using hierarchical logistic regression that includes random site effects. All regression models mentioned above will be fitted with and without potential confounders including age, gender, ethnicity/race, smoking, BMI, nodule size, and any facility-level factors balanced during the randomization. For H3b, to examine whether among all participants with a lung nodule ≤ 15 mm, more intensive surveillance will be associated with a greater number of serious complications related to invasive procedures, similar strategy used for H3a will be adopted. We will model the number of serious procedure-related complications using mixed-effects Poisson regression models and the frequency of patients with any serious complications using hierarchical logistic regression models. For H3c, to investigate whether all participants with a lung nodule ≤ 15 mm, more intensive surveillance will be associated with greater total exposure to diagnostic radiation than less intensive surveillance, we will use mixed effects models and log-transform the radiation exposure to make normal assumption more appropriate.

For H4, binary variables will be generated to indicate adherence to the recommended protocols measured at the level of the ordering provider and the patient. Cross tabulations of the

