Appendix C: Surveillance Protocols

Table C1: Surveillance protocol for incidental nodules, Group A, more intensive surveillance

Patient and Nodule characteristics		Surveillance times (months from index CT)
Solid, with Risk Factors		
≤4		12
>4 to ≤6		6, 18
>6 to ≤8		3, 9, 21 to 24
>8		3, 9, 21 to 24 or PET or tissue
Solid, without Risk Factors		
≤4		Optional (12)
>4 to ≤5		12
>5 to ≤8		6, 18
>8		3, 9, 21 to 24 or PET or tissue
Part-solid		
Solitary, solid component ≤5		3, 15, 27, 39
Solitary, solid component >5		3, tissue if persists
Multiple, solid component ≤5		3, 15, 27, 39
Multiple, solid component >5		3, tissue if persists and solid ≥5
Non-solid		
≤5, solitary		None
>5, solitary		3, 15, 27, 39
≤5, multiple		24, 48
>5, multiple		3, 15, 27, 39

Table C2: Surveillance protocol for incidental nodules, Group B, Less intensive surveillance

Nodule characteristics	Surveillance times (months from index CT)
Solid	
<6, solitary or multiple	None (Optional at 12 months in patients with risk factors)
≥6 to ≤8, solitary	12, 24
≥6 to ≤8, multiple	6, 18
>8, solitary or multiple	3, 15, 27 or PET or tissue
Part-solid	
<6, solitary	None
<6, multiple	6, 24, 48
≥6, solid component <6	6, 18, 30, 42, 54, 66
≥6, solid component ≥6	6, tissue if persists
Non-solid	
<6, solitary	None
≥6, solitary	12, 36, 60
<6, multiple	6, 24, 48
≥6, multiple	6, 24, 48

Table C3: Surveillance protocols for screening-detected nodules

Lung-RADS Category	Nodule characteristics	Surveillance times (months from index CT)		
		Group A	Group B	
1	No nodule	12, 24...	12, 24...	
	Calcified nodule			
	Fat-containing nodule			
2	Solid nodule <4	12, 24...	12, 24...	
	Solid nodule <6	6, 18, 30...		
	New solid nodule <4			
	Part-solid nodule <6			
	Non-solid nodule <20			
	Non-solid nodule ≥20, unchanged or slow-growing			
	Category 3 or 4 nodule unchanged for >3 months			
3	Solid nodule ≥6 to <8	3, 15, 27...	6, 18, 30...	
	New solid nodule, ≥4 to <6			
	Part-solid nodule ≥6, with solid component <6			
	Part-solid nodule, new <6			
	Non-solid nodule ≥20			
4A	Solid nodule ≥8 to <15	3, 9, 21... (PET may be used when solid component ≥8)	3, 15, 27... (PET may be used when solid component ≥8)	
	Solid nodule, new ≥6 to <8, or growing <8			
	Part-solid nodule ≥6, with solid component ≥6 to <8			
	Part-solid nodule, new or growing, with solid component <4			
	Endobronchial nodule			
4B	Solid nodule ≥15	CT at 3 months, PET or tissue, depending on probability of cancer and comorbidities		

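### H3c takes the log of a post-baseline radiation dose that is zero for patients with no later imaging, probably more of them in the less intensive arm, and gives no rule for the zeros

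*Combined protocol and SAP*

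**What the plan says.** - **Model.** In the Analysis Plan under Aim 3, the H3c text reads "we will use mixed effects models and log-transform the radiation exposure to make normal assumption more appropriate". It gives no offset, two-part model or other rule for zero doses.
- **Endpoint.** Primary endpoints, Aim 3, item 3 is cumulative dose, measured both as DLP and as effective dose: "Including radiation exposure from surveillance and diagnostic imaging following baseline CT scan through 2 years of follow-up". Imaging at 24 months counts; the baseline CT does not.
- **Summation.** Aim 3 Outcomes calculates effective dose per examination and has it "summed over the study period for each enrollee".
- **Population.** Inclusion Criteria: "The intention to treat population will include patients with nodules of this size who do or do not undergo surveillance imaging". The Analysis Plan applies intention to treat to all primary analyses, and H3c is stated for all participants with a nodule of 15 mm or less: "more intensive surveillance will be associated with greater total exposure to diagnostic radiation than less intensive surveillance".
- **Schedules.** For incidental solid nodules under 6 mm in Group B, Appendix C, Table C2 gives "None (Optional at 12 months in patients with risk factors"). It also recommends no CT for solitary part-solid nodules under 6 mm. Table C1 (Group A) schedules CT for most of these nodules.
- **Planned contrast.** Interventions to be compared: "The comparators selected will result in approximately 30% less imaging in the less intensive Group B".

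**The concern.** A patient with no imaging after the index CT has a cumulative dose of exactly zero, and the log of zero does not exist. The stated model therefore fails for part of the population it is meant to cover, and someone must choose a repair after the data are in, in an unblinded trial.

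Neither obvious repair is safe:

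- **Dropping the zeros** conditions on something that happens after randomization. It removes the patients spared all later radiation and so generally understates the dose saving.
- **Adding a constant** makes the answer depend on the constant and on the unit, and the endpoint is defined in two units.

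H3c is a listed Aim 3 primary endpoint, though not the Aim 1 primary outcome. Radiation is one of the harms the trial weighs against earlier diagnosis, so the size of the saving matters as well as its sign.

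**Working it through.** The plan states no power or effect figure for H3c, so there is none to reproduce. The undefined log follows from the text alone. The arithmetic below only illustrates how far the unspecified choice can move the result.

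**Does any other text handle the zeros?** The any-exam logistic models and the Poisson count models belong to H3a; they keep zeros but do not analyse dose. Multiple imputation (Missing Data) is for missing values, and a true zero is not missing.

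**Are the zeros balanced?** Not by design. Group B has no scheduled CT for incidental solid nodules under 6 mm. Group A has scans for these, except that the scan is optional at 4 mm or less without risk factors. Group A also has no CT for solitary non-solid nodules of 5 mm or less. Small screening-detected nodules are scanned in both arms (Table C3). These points narrow the imbalance without removing it.

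**Inputs for the illustration** (incidental solid nodules, 400,000 simulated patients per arm)

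- Scheduled scans to month 24, Group A with risk factors: 1, 2, 3, 3 for ≤4, >4–6, >6–8, >8 mm. Without: optional, 1, 2, 3 for ≤4, >4–5, >5–8, >8 mm (Table C1).
- Group B: 0 below 6 mm (one optional with risk factors), otherwise 2 (Table C2).
- Risk-factor share 52%, from 48% never smokers in the preliminary data.
- Assumed: 30–60% of nodules under 6 mm; 25–40% over 8 mm; 60–90% completion of each scheduled scan (central 73%, the same in both arms); optional scan done in 10–60%; dose per scan with median 2 mSv and log-SD 0.6.
- Off-schedule scans: Poisson, same mean in both arms, solved so that Group B has 30% less imaging in total.

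**Dropping zeros.** With p the zero share,

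true mean ratio = [(1 − p_B)/(1 − p_A)] × mean ratio among those imaged.

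A central run (45% under 6 mm, 33% over 8 mm, optional scan done in 35%) gave p_A = 7.6% and p_B = 21.4%. So (1 − 0.214)/(1 − 0.076) = 0.851, and 0.70/0.851 = 0.82 among those imaged. The log model without zeros compares mean log doses of 1.307 (B) and 1.512 (A): exp(1.307 − 1.512) = 0.81. The spread of assumptions gives 0.82 at its centre, or 0.80 if nodule size is also adjusted for.

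**Adding a constant c.** For small c,

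ratio ≈ exp[(1 − p_B)·m_B − (1 − p_A)·m_A + (p_B − p_A)·ln c],

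where m is the mean log dose among those imaged. One DLP unit is 0.01–0.02 mSv at assumed conversion factors of 0.01–0.02. At c = 0.015 mSv: 0.786 × 1.307 − 0.924 × 1.512 + 0.138 × (−4.200) = 1.027 − 1.397 − 0.580 = −0.950, and exp(−0.950) = 0.39. The third term comes from the analyst's constant alone.

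| Setting | Zeros A / B | True mean ratio | Zeros dropped | 1 mSv added | One DLP unit added |
|---|---|---|---|---|---|
| Central | 7% / 21% | 0.70 | 0.82 | 0.70 | 0.37–0.41 |
| 81 runs, total imaging 30% lower in B | 2–14% / 12–29% | 0.70 | 0.75–0.87 | – | – |
| 27 runs, no off-schedule imaging, 33% over 8 mm | – | 0.44–0.67 | 0.82–0.93 | – | – |

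**Unequal completion.** H4 expects worse adherence in Group A. With per-scan completion of 65% (A) and 80% (B), other inputs central and essentially no off-schedule imaging, a true ratio of 0.70 is read as 0.97 after dropping zeros.

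**Different assumptions.** Take 27% zeros in Group A, a geometric mean dose of 3 mSv, log-SD 0.8 and a true ratio of 0.70. Dropping zeros gives 0.70 if none of the reduction comes from zeros, 0.83 if half does, and 1.00 if all does. In that last case, adding 1, 0.1, 0.01 or 0.001 mSv gives 0.73, 0.47, 0.29 or 0.18.

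**Remedy.** A quasi-Poisson log-link model with site-clustered errors, zeros included (24 sites of 700 patients, 40 replicates), returned a mean ratio of 0.70.

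**The case against.** - **Some of this is already planned.** The plan promises descriptive dose statistics by site and arm, and nothing there excludes zeros. The H3a any-exam models resemble half of a two-part analysis. This stands, but neither gives a clustered comparison of dose that keeps zeros.
- **The index CT may be meant to count.** Aim 3 Outcomes sums dose over the study period and starts the surveillance period at the index CT, and Table 4 refers to total exposure and all CT scans. If the index CT counts, there are no zeros. The endpoint definition is the more specific text and excludes it. The inconsistency is real and needs its own correction.
- **Dose data are not collected in full on everyone.** Detailed exposure comes mainly from a random sample of roughly 22,000 California participants. This narrows the set analysed but does not remove patients with zero dose.
- **The size is uncertain.** The 73% completion per scan borrows an overall non-adherence figure of 27%; applied per scan, it implies only 0.73³ = 39% completing a three-scan schedule. Off-schedule imaging is solved for, not documented. With two off-schedule scans per patient, zeros fall to 2% and 6%, and a true ratio of about 0.81 is read as 0.82 after dropping zeros, although imaging is then no longer 30% lower in Group B. Screening-detected, subsolid and multiple nodules are not modelled. All of this stands against the magnitudes, not against the undefined log.
- **The model is a matter of choice.** A two-part primary analysis would also be defensible. The essential request is a stated rule for zeros.

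**Conclusion.** The concern holds: the H3c model is wrong as written, because it is undefined for patients whom the plan itself keeps in the analysis. That conclusion needs only that some participants have no imaging after baseline.

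The size is an illustration. With imaging 30% lower in Group B and equal completion in both arms, a true mean-dose ratio of 0.70 is read as 0.75 to 0.87 when zeros are dropped. One DLP unit added to every dose gives about 0.4 in the central case. The direction did not reverse in the equal-completion runs, but the reading of 0.97 under unequal completion shows that it is not assured. Heavy off-schedule imaging would nearly remove the error from dropping zeros. Confidence is high on the missing rule and much lower on any single figure. This should be fixed before analysis; it does not touch the Aim 1 primary outcome.

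**What to change.** 1. In the H3c analysis text, state that all participants in the dose sample are analysed, zeros included. Compare mean cumulative post-baseline dose between arms with a log-link model that accepts zeros (quasi-Poisson or Tweedie), clustered by site.
2. As a secondary summary, report a two-part analysis: any imaging (logistic), and log dose among those imaged, labelled as conditional on imaging. The present log model is kept as the second part.
3. In Aim 3 Outcomes, state that the index CT is excluded from the sum, to agree with the endpoint definition.

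The cost is two sentences in the analysis plan and a few words in the outcomes section. No new data are needed.
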